8.1 Site monitoring

Before study initiation, at a site initiation visit or at an investigator's meeting, a Novartis representative will review the protocol and data capture requirements (i.e. eCRFs) with the investigators and their staff. During the study, Novartis employs several methods of ensuring protocol and Good Clinical Practice (GCP) compliance and the quality/integrity of the sites' data. The field monitor will visit the site to check the completeness of patient records, the accuracy of data capture / data entry, the adherence to the protocol and to GCP, the progress of enrollment, and to ensure that study treatment is being stored, dispensed, and accounted for according to specifications. Key study personnel must be available to assist the field monitor during these visits. Continuous remote monitoring of each site's data may be performed by a centralized Novartis CRA organization. Additionally, a central analytics organization may analyze data and identify risks & trends for site operational parameters and provide reports to Novartis Clinical Teams to assist with trial oversight.

The investigator must maintain source documents for each subject in the study, consisting of case and visit notes (hospital or clinic medical records) containing demographic and medical information, laboratory data, electrocardiograms (ECGs), and the results of any other tests or assessments. All information on CRFs must be traceable to these source documents in the subject's file. The investigator must also keep the original informed consent form signed by the patient (a signed copy is given to the subject).

The investigator must give the monitor access to all relevant source documents to confirm their consistency with the data capture and/or CRF entries. Novartis monitoring standards require full verification for the presence of informed consent, adherence to the inclusion/exclusion criteria, documentation of SAEs, and of data that will be used for all primary variables. Additional checks of the consistency of the source data with the CRFs are performed according to the study-specific monitoring plan. No information in source documents about the identity of the subjects will be disclosed.

8.2 Data collection

Designated investigator staff will enter the data required by the protocol into the OC/RDC system. Designated investigator site staff will not be given access to the system until they have been trained.

Automatic validation procedures within the system check for data discrepancies during and after data entry and, by generating appropriate error messages, allow the data to be confirmed or corrected online by the designated investigator site staff. The Investigator must certify that the data entered into the electronic Case Report Forms are complete and accurate. After database lock, the investigator will receive copies of the patient data for archiving at the investigational site.

8.3 Database management and quality control

Data from the CRFs are entered into the study database by Novartis Data Management staff using single data entry and by referring to the scanned image of the CRF.

Novartis staff review the data entered into the CRFs by investigational staff for completeness and accuracy and instruct the site personnel to make any required corrections or additions. Queries are sent to the investigational site using an electronic data query. Designated investigator site staff is required to respond to the query and confirm or correct the data. If the electronic query system is not used, a paper Data Query Form will be faxed to the site. Site personnel will complete and sign the faxed copy and fax it back to Novartis staff that will make the correction to the database. The signed copy of the Data Query Form is kept at the investigator site.

Concomitant medications entered into the database will be coded using the World health Organization (WHO) Drug Reference List, which employs the Anatomical Therapeutic Chemical classification system. Concomitant procedures, non-drug therapies and AEs will be coded using the Medical Dictionary for Regulatory Activities (MedDRA) terminology.

Laboratory samples will be processed centrally and the results will be sent electronically to Novartis (or a designated CRO).

Patients/subjects will fill in their PRO data in a site based tablet. The system will be supplied by a vendor(s), who will also manage the database. The database will be sent electronically to Novartis personnel (or designated CRO).

Randomization codes and data about all study drug(s) dispensed to the patient and all dosage changes will be tracked using an IRT system. The system will be supplied by Novartis, who will also manage the database. Each occurrence of a code break via IRT will be reported to the clinical team and monitor. The code break functionality will remain available until study shut down or upon request of Novartis.

The occurrence of relevant protocol deviations will be determined. After these actions have been completed and the database has been declared to be complete and accurate, it will be locked and the treatment codes will be unblinded and made available for data analysis. Any changes to the database after that time can only be made after written agreement by Novartis Development management.

8.4 Data Monitoring Committee

A Data Monitoring Committee is not planned for this study.

8.5 Adjudication Committee

An independent external adjudication committee may be used to monitor specific safety events, including, but not limited to clinically significant cardio- and cerebrovascular events. The events will be reviewed and adjudicated in a blinded fashion as they occur during the conduct of the trial.

Details regarding the definition of AEs of special interest as well as the adjudication process will be available in the relevant secukinumab Adjudication Committee charter.

9 Data analysis

Summary statistics for continuous variables include N, mean, standard deviation, minimum, lower quartile, median, upper quartile, and maximum. For binary or discrete variables the absolute number of subjects in each category and relative frequencies will be provided.

Unless otherwise specified, p-values will be presented as 2-sided p-values and the type I error rate (alpha) will be 5%.

Inferential efficacy comparison of secukinumab 300mg with adalimumab will be performed at Week 52 unless otherwise specified.

Efficacy and safety data for the entire treatment period will be presented by treatment groups.

9.1 Analysis sets

The following analysis sets will be used in this trial:

Randomized set: The randomized set will be defined as all subjects who were randomized. Unless otherwise specified, mis-randomized subjects (mis-randomized in Interactive Voice Response (IVR)) will be excluded from the randomized set.

Mis-randomized subjects are defined as those subjects who were mistakenly randomized into the IVR prior to the site confirming all eligibility criteria had been met and to whom no study medication was given. Mis-randomized subjects are treated as screen failures.

Full analysis set (FAS): The FAS will be comprised of all subjects from the randomized set to whom study treatment has been assigned. Following the intent-to-treat principle, subjects will be analyzed according to the treatment assigned to at randomization.

Safety set: The safety set includes all subjects who took at least one dose of study treatment during the treatment period. Subjects will be evaluated according to treatment received.

9.2 Subject demographics and other baseline characteristics

Demographics and baseline characteristics

Summary statistics will be presented for continuous demographic and baseline characteristic variables for each treatment group and for all subjects in the randomized set. The number and percentage of subjects in each category will be presented for categorical variables for each treatment group and all subjects.

The following demographic variables and baseline disease characteristics will be summarized by treatment groups:

- Gender, age, race, ethnicity, weight, height, and BMI
- ACR components and other disease-related measures (e.g. presence of enthesitis, , time since first diagnosis of psoriatic arthritis, with psoriasis $\geq 3\%$).

Medical history

Any significant prior or active medical condition at the time of signing informed consent will be coded using the MedDRA dictionary. These medical conditions will be summarized by primary system organ class and preferred term.

To establish a baseline level of cardiovascular risk, the number and percentage of subjects with pre-solicited cardiovascular risk factors will be summarized by treatment group. The number of cardiovascular risk factors that each subject has will also be summarized by treatment group. If it is unknown whether or not a subject currently or previously experienced a specific cardiovascular risk factor, it will be assumed that cardiovascular risk factor did not occur for that subject.

9.3 **Treatments**

Study treatment

The analysis of study treatment data will be based on the safety set. The number of active injections received will be presented by treatment group.

The duration of exposure to study treatment will also be summarized by treatment group. In addition, the number and percentage of subjects with cumulative exposure levels (e.g. any exposure, ≥ 1 week, ≥ 2 weeks, ≥ 3 weeks, ≥ 4 weeks, ≥ 8 weeks, etc.) will be presented.

Prior and concomitant medication

Prior and concomitant medications (including Rescue medications defined in Section 5.5.6) will be summarized in separate tables by treatment group. Prior medications are defined as treatments taken and stopped prior to first dose of study treatment. Any medication given at least once between the day of first dose of randomized study treatment and the date of the last study visit will be a concomitant medication, including those which were started pre-baseline and continued to the period where study treatment is administered.

Medications will be presented in alphabetical order, by Anatomical Therapeutic Classification (ATC) codes and grouped by anatomical main group. Tables will show the overall number and percentage of subjects receiving at least one treatment of a particular ATC code and at least one treatment in a particular anatomical main group.

Significant prior and concomitant non-drug therapies and procedures will be summarized by primary system organ class and MedDRA preferred term.

The number and percentage of subjects receiving prior and concomitant PsA therapy will be presented by randomized treatment group as well as the reasons for stopping their therapies (primary lack of efficacy, secondary lack of efficacy, lack of tolerability, other).

9.4 Analysis of the primary variable(s)

Details of the testing strategy including primary and secondary endpoints are provided in Section 9.5.1.

9.4.1 Variable(s)

The primary efficacy endpoint will be ACR20 response at Week 52 for superiority test to compare 300 mg secukinumab with adalimumab. The analysis of the primary efficacy endpoint will be based on the FAS subjects. Primarily, CRP will be used instead of ESR to calculate ACR response; ESR will only be used in the event CRP is missing.

Statistical model, hypothesis, and method of analysis 9.4.2

The statistical hypothesis for ACR20 being tested for superiority test is that there is no difference in the proportion of subjects fulfilling the ACR20 criteria at Week 52 in the secukinumab 300 mg group vs. adalimumab.

Let pj denote the proportion of ACR20 responders at Week 52 for treatment regimens j, j=0, 1 where

0 corresponds to adalimumab,

1 corresponds to secukinumab 300 mg

In statistical terms, H1: p1 = p0, HA1: $p1 \neq p0$, i.e.

H1: secukinumab is not different to adalimumab regimen for signs and symptoms (ACR20 response) at Week 52.

The primary endpoint of ACR20 at Week 52 in the FAS will be evaluated using a logistic regression model with treatment as a factor and weight as a covariate. Odds ratios will be computed for comparisons of secukinumab 300 mg vs. adalimumab regimen utilizing the logistic regression model fitted.

9.4.3 Handling of missing values/censoring/discontinuations

The primary and secondary estimands focus on the difference between the treatment groups in the proportion of patients achieving monotherapy ACR20 response (or other response variables) at week 52 in FAS patients. Monotherapy response is defined as achieving the requirements for the clinical response (e.g. ACR20) and not prematurely discontinuing study medication and not taking concomitant MTX/cDMARD (composite estimands). Missing data for ACR20 response and other binary efficacy variables (e.g. ACR50, , PASI90, etc.) for data up to Week 52 will be handled by multiple imputation. Multiple imputation (MI) is a simulation based approach where missing values are replaced by multiple Bayesian draws from the conditional distribution of missing data given the observed data and covariates, creating multiple completed data sets. These completed data sets can then be analyzed using standard

methods. Within this analysis the ACR composites or PASI score will be imputed and response variables will be derived based on the imputed scores. In the multiple imputation analysis the response status will be imputed based on the individual treatment arm information.

Continuous variables (e.g. ACR components, DAS, etc.) will be analyzed using a mixed-effects repeated measures model (MMRM) which is valid under the missing at random (MAR) assumption. For analyses of these parameters, if all post-BSL values are missing then these missing values will not be imputed and this subject will be removed from the analysis of the corresponding variable, i.e. it might be that the number of subjects providing data to an analysis is smaller than the number of subjects in the FAS.

9.4.4 Supportive analyses

Sensitivity analyses and supportive analyses will be conducted in order to provide evidence that the results seen from the primary analysis are robust. These analyses will center on the deviations in model assumptions, and the treatment of missing data.

In order to determine the robustness of the logistic regression model used for the primary analysis, ACR20 response at Week 52 may also be evaluated using a non-parametric regression (Koch 1998) model with the same independent variables as the logistic regression model. In addition, further logistic regression models may be conducted which explore the impact of other BSL or disease characteristics on response.

The impact of missing data on the analysis results will be assessed as well by repeating the logistic regression model using ways to handle missing data. These may include, but are not limited to:

Non-responder Imputation

Observed data analysis

Additional sensitivity analyses will be conducted to examine the effect of taking concomitant treatment of MTX and/or other cDMARDs along with study drug and/or the effect of treatment discontinuation without rescue medication but remaining in the study on the primary endpoint.

9.5 Analysis of secondary variables

9.5.1 Efficacy variables

The secondary efficacy endpoints are listed below. Secondary efficacy endpoints will be analyzed using the FAS population unless otherwise specified.

- PASI90 response at Week 52 in Superiority test for secukinumab 300 mg
- ACR50 response at Week 52 in Superiority test for secukinumab 300 mg
- Change from baseline in HAQ-DI[©] score at Week 52 in Superiority test for secukinumab 300 mg
- Resolution of enthesitis at Week 52 in Superiority test for secukinumab 300 mg

Testing strategy

The following hypotheses will be included in the hierarchical testing strategy, and type-I-errors will be set such that family-wise two-sided type-I-error of 5% is kept. The inferential testing procedure will only continue if the previous test was rejected at the appropriate type-I-error rate as specified after Figure 9-1.

Primary objectives (detailed in Section 9.4.2)

[figure not shown]
• H₁: secukinumab 300 mg is not different to adalimumab regimen with respect to ACR20 response at Week 52.

Secondary objectives

The same method of imputation for binary endpoints that is being used for the primary is also being used for secondary endpoints

- H₂: secukinumab 300 mg is not different to adalimumab regimen with respect to PASI90 response at Week 52
- H₃: secukinumab 300 mg is not different to adalimumab regimen with respect to ACR50 response at Week 52
- H₄: secukinumab 300 mg is not different to adalimumab regimen with respect to the change from baseline in HAQ-DI[©] at Week 52
- H₅: secukinumab 300 mg is not different to adalimumab regimen with respect to resolution of enthesitis at Week 52

Figure 9-1 Testing Strategy

- The family-wise error rate will be set to two-sided α =5% and it will be controlled with the proposed hierarchical testing strategy.
 - If H1 is rejected at α , the hypothesis H2 will be tested at α . If H2 is rejected at α , H3 will be tested at α and so on.

ACR50 at Week 52

Response at Week 52 to ACR50 in the FAS will be evaluated using a logistic regression model with treatment as a factor and weight as a covariate.

PASI90 response

[figure not shown]
PASI90 response at Week 52 will be evaluated using a logistic regression model with treatment as a factor and weight as a covariate.

Physical function (HAQ-DI[©])

Between-treatment differences in the change in HAQ-DI[©] will be evaluated using a MMRM with treatment regimen, analysis visit as factors, and weight and baseline HAQ-DI[©] score as continuous covariates. Treatment by analysis visit and baseline by analysis visit will be included as interaction terms in the model. An unstructured covariance structure will be assumed for this model. The significance of the treatment effects for secukinumab regimens at different analysis visits will be determined from the pairwise comparisons performed between secukinumab regimen and adalimumab at the appropriate analysis visits.

Resolution of enthesitis

Resolution (presence to absence) of enthesitis at Week 52 will be evaluated using a logistic regression model with treatment as a factor and weight as a covariate.

9.5.3 Safety variables

Adverse events

Treatment-emergent AEs (TEAEs, adverse events that started after the first dose of study treatment or events present prior to the first dose of study treatment but increased in severity based on preferred term) will be summarized up to 12 weeks (84 days) after the last dose. Non-treatment-emergent AEs will be listed in a listing but not summarized.

TEAEs will be summarized by presenting, for each treatment group, the number and percentage of subjects having any AE, having an AE in each primary system organ class and having each individual AE (preferred term). Summaries will also be presented for AEs by severity and for study treatment related AEs. If a subject reported more than one AE with the same preferred term, the AE with the greatest severity will be presented. If a subject reported more than one AE within the same primary system organ class, the subject will be counted only once with the greatest severity at the system organ class level, where applicable. SAEs will also be summarized.

As appropriate, the incidence of AEs will be presented per 100 subject-years of exposure.

Separate summaries will be provided for death, SAE, other TEAEs leading to study treatment interruption or study treatment discontinuation.

A graphical display of relative frequencies within system organ classes and relative risks, as appropriate, will be presented.

When adjudication is required of major cardiovascular events, a summary of those types of events as reported by the investigator and confirmed by adjudication will be provided.

Laboratory data

The summary of laboratory evaluations will be presented for three groups of laboratory tests (hematology, serum chemistry and urinalysis). Descriptive summary statistics for the change from baseline to each study visit will be presented. These descriptive summaries will be presented by test group, laboratory test and treatment group. Change from baseline will only be summarized for subjects with both baseline and post-baseline.

For each parameter, the maximum change from baseline within each study period will be evaluated analogously.

In addition, shift tables will be provided for all parameters to compare a subject's baseline laboratory evaluation relative to the visit's observed value. For the shift tables, the normal laboratory ranges will be used to evaluate whether a particular laboratory test value was normal, low, or high for each visit value relative to whether or not the baseline value was normal, low, or high. These summaries will be presented by laboratory test and treatment group. Shifts will be presented by visit as well as for most extreme values post-baseline.

Vital signs

Analysis of the vital sign measurements using summary statistics for the change from baseline for each post-baseline visit will be performed. These descriptive summaries will be presented by vital sign and treatment group. Change from baseline will only be summarized for subjects with both baseline and post-baseline values.

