In Section 9.4.3, the latter part of the first sentence, regardless of adherence to randomized treatment" has been deleted. Additional changes to the sentence have been made to clarify the estimand and the definition of monotherapy response has been added.

In the second paragraph of Section 9.4.4, "ACR20 response at Week 52 will also be evaluated" has been changed to "ACR20 response at Week 52 may also be evaluated".

In the last paragraph of Section 9.4.4, "and the effect of treatment discontinuation without rescue medication" has been changed to "and/or the effect of treatment discontinuation without rescue medication".

Institutional Review Board (IRBs)/Independent Ethics Committee (IECs) and Health Authorities

A copy of this amended protocol will be sent to the Institutional Review Board (IRBs)/Independent Ethics Committee (IECs) and Health Authorities.

The changes described in this amended protocol are non-substantial and do not require IRB/IEC approval prior to implementation.

The changes herein do NOT affect the trial specific model ICF.

Amendment 01

Amendment rationale

At the time of this amendment no subjects have been randomized in the study. No change to the study population is proposed by this amendment.

This protocol amendment is primarily issued for the following reasons:

- 1. The half-life of adalimumab is reported to be approximately 2 weeks, therefore in the original protocol the safety follow-up was planned to cover 5 x the half-life or approximately 10 weeks. Consequently, the safety follow-up visit was scheduled for 10 weeks after last dose of adalimumab. Some Health Authorities have mandated that the safety follow-up for adalimumab be extended to 4 months after last dose of adalimumab, to be consistent with the Humira® SmPC 2016.
- 2. Exclusion Criteria 2 provided guidelines and examples where local label requirements for contraception use, after the last dose of study treatment, should be followed by women of childbearing potential. Health Authority requests have been received that the protocol should specify contraception use for five months after last dose of adalimumab (see Humira[®] SmPC 2016).

Changes to the protocol

Changes to specific sections of the protocol are shown in the track changes version of the protocol using strike through red font for deletions and red underlined for insertions.

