5.5.13 Study completion and post-study treatment

A subject will be considered to have completed the study when the subject has completed the last visit planned in the protocol..

Information on the subject's completion or discontinuation of the study and the reason for discontinuation of the study will be recorded on the appropriate Study Phase Completion eCRF.

In any case, the investigator or site staff must contact the IRT as soon as possible to record the subject's study completion and/or discontinuation.

The investigator must provide follow-up medical care for all subjects who are prematurely withdrawn from the study, or must refer them for appropriate ongoing care. This care may include initiating another treatment outside of the study as deemed appropriate by the investigator. This treatment may be any non-biologic DMARD. In case of a biologic treatment, a waiting period of 4 months before initiating the treatment is recommended; elimination of adalimumab may take up to four months (Humira® SmPC 2016).

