¹³ Subjects who discontinue the study should be scheduled for an End-of-Study study visit, 4 weeks after their last study treatment administration, at which time all of the assessments listed for the Week 52 visit will be performed. Subjects will return to the study site for the follow-up visits at 12 weeks and 18 weeks after last study treatment (assessments as listed for Week 60 and Week 68).S = assessment to be recorded on source documentation

^{*}The administration of s.c. study treatment may be done at site or at the subject's home by an independent drug administrator. Concomitant medication/non-drug therapy and Adverse Events/SAEs will be collected by telephone, if the administration of study treatment is done at home.

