2.5 Treatments (study treatment, rescue medication, concomitant therapies, compliance)

2.5.1 Study treatment / compliance

The analysis of study treatment data will be based on the safety set. The duration of exposure to study treatment will also be summarized by treatment group. In addition, the number and percentage of subjects with cumulative exposure levels (e.g. any exposure, ≥ 1 week, ≥ 2 weeks, ≥ 3 weeks, ≥ 4 weeks, ≥ 8 weeks, etc.) will be presented.

Duration of exposure of a treatment will be defined as the time from first dose of the treatment to the minimum of (last dose of the treatment + 84 days) and (last visit date).

Duration of exposure (years) = duration of exposure (days) / 365.25

Duration of exposure (100 subject years) = duration of exposure (years) / 100

The analyses of duration of exposure described above will be done for the entire study treatment period.

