2.9.1 Adverse events (AEs)

The crude incidence of treatment emergent adverse events (TEAEs) (i.e. events started after the first dose of study treatment or events present prior to the first dose of study treatment but increased in severity based on preferred term and on or before last dose + 84 days) will be summarized by primary system organ class and preferred term. Confidence intervals for the crude rate will be derived as described in [Section 5.2.4.1](#). Graphical displays of the crude incidence rates will be presented for all AEs and serious AEs by system organ class.

Adverse events reported will be presented first by alphabetical order of system organ class and then in descending frequency according to its incidence in secukinumab group starting from the most common event. For ties in incidence rate of secukinumab group, sort adverse events by incidence rate of adalimumab group. Summaries (crude incidences only) will also be presented for AEs by severity and for study treatment related AEs. If a particular AE 'severity' is missing, this variable will be listed as missing and treated as missing in summaries. If a subject reported more than one adverse event with the same preferred term, the adverse event with the greatest severity will be presented. If a subject reported more than one adverse event within the same primary system organ class, the subject will be counted only once with the greatest severity at the system organ class level, where applicable.

Separate summaries will be provided for adverse events suspected to be related to study drug, deaths, serious adverse events, and adverse events leading to discontinuation and adverse events leading to temporary dose interruption.

Adverse events will also be reported separately by SMQ according to MedDRA. The MedDRA version used for reporting the study will be described in a footnote.

Non-treatment emergent adverse events will be listed.

Algorithms for date imputations will be provided in RAP Programming Dataset Specification (PDS).

For serious adverse events (SAEs) occurred during screening a listing will be prepared for all subjects screened including screening failures.

When adjudication is required of major cardiovascular events, a listing of those types of events as reported by the investigator and confirmed by adjudication will be provided.

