The safety analyses that will be performed for treatment emergent AEs and on treatment labs, ECG and vital signs for the analysis period is described in [Table 2-1](#).

Table 2-1 Overview of analyses on some safety endpoints

Analysis period	AEs & SAEs	AEs by severity	Study-drug related AEs	Risk	Notables for (vitals/ECG), lab criteria
Entire treatment	Cruide incidence	Cruide incidence	Cruide incidence	Cruide incidence	Cruide incidence

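### Do the adverse-event summaries stop too early, at 84 days after the last dose, when patients are followed for 126 days?

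*Protocol*

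**What the plan says.** Protocol 9.5.3 states that treatment-emergent events "will be summarized up to 12 weeks (84 days) after the last dose", and then: "Non-treatment-emergent AEs will be listed in a listing but not summarized". SAP 2.9.1 makes the limit part of the definition. An event counts if it started after the first dose, or was present earlier but "increased in severity based on preferred term and on or before last dose + 84 days". Events outside the definition are listed. SAP 2.5.1 ends exposure at "the minimum of (last dose of the treatment + 84 days) and (last visit date"), whichever comes first. SAP 2.5.2, 2.9.2 and 2.9.3 use 84 days again for concomitant medication, laboratory data and vital signs.

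Collection runs longer. Protocol 3.1 puts the last adalimumab injection at Week 50 and the follow-up visits at Weeks 60 and 68. Protocol 7.1 collects adverse events until the end of the study. For patients who leave the study early, Protocol Section 6 schedules "follow-up visits at 12 weeks and 18 weeks after last study treatment".

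**The concern.** The Amendment 01 rationale explains the longer follow-up: "Some Health Authorities have mandated that the safety follow-up for adalimumab be extended to 4 months after last dose of adalimumab". Protocol 5.5.13 still gives the reason, that "elimination of adalimumab may take up to four months". Follow-up now lasts about four months after the last dose, yet the summary window is 12 weeks. It is natural to suspect that the visits were moved and the analysis window was forgotten.

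Comparative safety is a secondary objective (Protocol 2.2) and there is no data monitoring committee (Protocol 8.4). If the late events mattered, a reader would have only a listing for them, without counts or exposure time by arm. The sentence introducing SAP Table 2-1, "The safety analyses that will be performed for treatment emergent AEs and on treatment labs", leads into a table that includes serious events, so the limit seems to reach them too.

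**Working it through.** **Inputs.** Last dosing visit Week 50 (Protocol 3.1, SAP 2.6.1); last follow-up visit Week 68 (Protocol 3.1); window 84 days (Protocol 9.5.3, SAP 2.9.1); 850 patients (Protocol 3.1); adalimumab half-life about two weeks (Amendment 01 rationale). Retention and serious-event rates are not in the documents, so both are assumed below.

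**1. The window.** The plan's figure reproduces: 12 × 7 = 84 days. With study day = 7 × week + 1:
- Week 50 is Day 351.
- The window closes on Day 351 + 84 = Day 435, which is Week 62.
- Week 68 is Day 477, and 477 − 351 = 126 days (18 weeks).
- Outside the window: 126 − 84 = 42 days, or 42/126 = 33%.
- The Week 60 visit, 70 days after Week 50, falls inside the window; the Week 68 visit falls outside.

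**2. Time left out.** If every patient is dosed through Week 50 and followed to Week 68:
- Outside: 850 × 42/365.25 = 97.7 patient-years.
- Inside: 850 × (350 + 84)/365.25 = 1,010.0 patient-years.
- Ratio: 97.7/1,010.0 = 9.7%.
- If 70%, 80% or 90% are followed that long (assumption): 68.4, 78.2 or 88.0 patient-years outside.

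**3. Events left out.** At an assumed 5 to 10 serious events per 100 patient-years:
- Ceiling: 97.7 × 0.05 = 4.9 to 97.7 × 0.10 = 9.8 serious events, both arms together.
- With 70% to 90% followed: 68.4 × 0.05 = 3.4 to 88.0 × 0.10 = 8.8, so about 2 to 4 per arm.

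**4. Drug remaining.** 84/14 = 6 half-lives, and 0.5^6 = 1.6%. 126/14 = 9 half-lives, and 0.5^9 = 0.2%. The extra 42 days are therefore observed at very low drug levels.

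**5. Early stoppers.** Patients who stop treatment but keep attending have more time outside the window: (68 − stopping week) × 7 − 84, which is 308, 224 or 140 days for stopping at Week 12, 24 or 36. Protocol 5.5.9 lets these patients use otherwise prohibited medication. Here the limit helps, because it keeps long off-drug time out of the comparison of the randomised drugs.

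**6. Consistency.** The SAP describes the Week 60 and 68 visits (1.1) and applies 84 days to adverse events, exposure, concomitant medication, laboratory data and vital signs. For concomitant medication it chose 84 days although Protocol 9.3 runs to the last study visit. That pattern points to a deliberate rule. Event counts and exposure end at the same point, so a rate per patient-year has matching numerator and denominator.

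**The case for a change.** The strongest case for acting is that regulators asked for the longer follow-up, comparative safety is an objective, and one supplementary table set, capped at last injection + 126 days with matching exposure, would cost little. Protocol 9.6 also says the final analysis will include follow-up data, and a listing gives neither counts by arm nor a denominator.

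Some of this stands. No visible section defines a table for days 85 to 126, and such a table would do no harm if labelled supplementary. But a listing satisfies Protocol 9.6, and collecting data for longer than the treatment-emergent window is not itself inconsistent. The four-month elimination statement governs live vaccines (Protocol 5.5.5) and the wait before a new biologic (5.5.13); it does not set the period for attributing adverse events.

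The argument that the window once covered all follow-up rests on superseded text in the amendment log. It also cuts the other way. Eighty-four days already exceeded the earlier 10 weeks (70 days), so on that reading the window was never tied to the last visit.

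Two uncertainties remain. The separate death and serious-event summaries in Protocol 9.5.3 and SAP 2.9.1 state no window of their own, so it is not established that the limit applies to them. And the public SAP skips from 2.7 to 2.9 and from 2.9.3 to 2.12.3, so a later-window table may exist in text that was removed.

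The secukinumab arm's Week 50 injection is placebo. If the last dose meant the last active dose, that arm's window would close at Week 60 and leave 56 days outside instead of 42. The protocol glossary and 5.5.4 count placebo as study treatment, and SAP 2.6.1 names Week 50 as the last dosing visit, so the text already points to the same endpoint in both arms.

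**Conclusion.** The concern does not hold. The observation is accurate: on the nominal schedule, 42 of 126 post-dose days lie outside the summarised window. But the 84-day rule is explicit, symmetric between arms, matched to exposure and long relative to the stated half-life, and events after it are listed. Followed as written, the plan gives sound safety results.

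The time outside the window is at most 97.7 patient-years (9.7% on top of the 1,010 inside), or 68 to 88 if 70% to 90% of patients are followed for the full 126 days. The figure of about 5 to 10 serious events over both arms uses that 97.7-year ceiling and an assumed rate of 5 to 10 per 100 patient-years. A by-arm table for this period is a matter of preference. The conclusion rests on reading the last dose as the last study-treatment injection, placebo included.
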